5.2 Study Drug Return and Accountability

Study monitors [REDACTED] will conduct accountability of APP13007 and matching vehicle placebo. Accountability will be ascertained by performing reconciliation between the number of bottles of study drug, along with bottle ID numbers, sent to the site and the number of bottles dispensed (used), unused or un-dispensed (along with bottle ID numbers) at the time of reconciliation. In addition, the number of bottles of study drug (along with bottle ID numbers) dispensed and returned will also be accounted for.

Clinical trial materials will be shipped to the investigational sites under sealed conditions with a temperature tracking device. Study drugs shipment records will be verified by comparing the shipment inventory sheet to the actual quantity of study drug (number of bottles and bottle ID numbers) received at the site. Accurate records of receipt and disposition of the study drug (e.g., dates, number of bottles and each bottle ID number received, dispensed, lost or compromised, and returned) and subject number associated with the bottle ID number must be maintained by the Investigator or his/her designee. [REDACTED]

At the end of the study, all study materials, including any used (and returned) and unused study drugs bottles, even if empty, will be returned to the drug packaging and distribution vendor in accordance with Sponsor or designee's standard operations procedures (SOPs), following approval by the Sponsor. All returns of study drugs will be documented. The study monitor or designee will verify drug accountability. All drug accounting procedures must be completed before the study is considered complete.

5.3 Masking and Unmasking

The Sponsor, the management and project team at the CRO responsible for trial management, monitoring and data collection and management, the study monitors, the Study Medical Monitor, the study subjects, the Investigators and the study site staff responsible for managing and administering the study, communicating with the study subjects, and/or performing assessments of study endpoints will be masked to study treatment assignment of each subject throughout the entire study.

The Study Medical Monitor will remain masked throughout the study unless unmasked information becomes necessary as part of the management of a medical emergency or SAE for a particular subject, as described below.

A randomization schedule will be computer-generated by a qualified biostatistician independent of the study conduct and management and will be uploaded into the EDC system by a designated person not involved in the study conduct, data collection or management. The EDC/IWRS system will be used for randomization and unmasking of treatment assignment when necessary.

In case of a medical emergency or occurrence of an SAE, the Investigator will treat each subject as needed and should contact the Study Medical Monitor, if required, to discuss whether it is appropriate to unmask the subject to reveal the subject's treatment assignment. If deemed necessary, the Investigator will log into the EDC system to obtain unmasking information. The Investigator must use their individual login information to gain access to the unmasking information. The Investigator will also notify the IRB and the CRO managing and monitoring this study when treatment assignment for a particular subject is unmasked. The Study Medical Monitor will notify the Sponsor Medical Monitor when treatment assignment for a particular subject is unmasked due to a medical emergency or SAE. It is important to note that the study treatment assignment will be revealed only on a subject-by-subject basis and the treatment assignment of the other subjects in the study, as described above, will remain masked until the final database is locked. Once the treatment assignment for a specific subject is unmasked, it will be made available to the Investigator and the Sponsor. Other personnel involved in the monitoring or conduct of this study will remain masked.

5.4 Prior/Concomitant Therapy and Rescue Medication

All prior/concomitant medications (prescription and OTC) a subject is receiving at the Screening visit and 90 days prior to the Screening visit and taken throughout the course of the study will be recorded as follows:

- Information regarding the duration of a prior/concomitant medication (including start and stop dates), dose, frequency, site of dosing (right eye, left eye, both eyes, non-ocular) and the reason why the prior/concomitant medication is being taken will be recorded in the source documents and in the Prior/Concomitant Medications (ConMeds) page of the eCRF.
- Medications used for the surgical procedure will be recorded in the source documents and in the ConMeds page of the eCRF.
- The ocular medications (mydriatics and topical analgesics) used to perform the dilated ophthalmoscopy and Goldmann applanation tonometry assessments will be recorded in the source documents only.

Note: The information on prior/concomitant medications will be used to determine whether a subject is taking or has taken prohibited medications as outlined in [Section 5.4.2](#).

5.4.1 Rescue Medication

Any subjects who have evidence of persistent or worsening inflammation as described in [Section 9.4](#) may be rescued and placed on appropriate alternate therapy. The choice of rescue medication is at the Investigator's discretion. Rescue medication should be entered into the eCRF with annotation indicating that the medication was used for rescue.

Rescued subjects will be considered as treatment failures, and the need for rescue therapy will not be considered an adverse event (AE). Rescued subjects will stop study drug and should not be withdrawn from the study, and will be assessed at each subsequent visit, if possible, through completion of the Visit 6 (POD22) assessments or until the Investigator has deemed the subject is stable and can be released from the study as detailed in [Section 6.3](#).

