⁹ The first dose of study drug should be instilled into the study eye at the clinic visit under supervision of clinic staff. The second dose on POD1 can be administered at home. Subjects who are rescued will not continue to instill study drug or receive further diary cards but will remain in the study to complete the procedures/assessments through Visit 6 (POD22).

¹⁰ The site must contact the subject via the subject's preferred method on POD14 to remind him/her not to instill study drug on POD15 and to bring the bottle of study drug and the dosing diary back to the site at the POD15 visit.

¹¹ Concomitant medications used for rescue should be reported in the eCRF.

[figure not shown]
¹² AEs and Concomitant Medications should only be recorded on Day 0 if they result in disqualification (i.e., screen failure) of the subject; otherwise, the AEs and Concomitant Medications applicable to Day 0 should be recorded when the subject returns for Visit 2 (POD1).

¹³ Any AEs reported to the site during the POD14 contact must be recorded in the source documents. Further assessment of any reported AEs may require an Unscheduled Visit on POD14 if medically significant or they may be assessed, as appropriate, during Visit 5 (POD15).

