6.2.10 Study Visit Schedule for Rescued Subjects

Subjects who are rescued as discussed in [Section 9.4](#) will discontinue study drug and receive rescue medication.

The Investigator should make every effort to keep subjects who are rescued in the study until they complete the Visit 6 (POD22) assessments ([Table 1](#)).

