9.0 SAFETY MANAGEMENT

9.1 Stopping Criteria

9.1.1 Individual Subject

9.1.1.1 Lack of Efficacy (See [Section 9.4](#))

The Investigator should consider whether to stop the study drug because of lack of efficacy and rescue the subject with alternative therapy (see [Section 9.4](#)).

Rescued subjects shall continue in the study and be assessed at each subsequent scheduled visit until Visit 6 (POD22). The study drug will be stopped as indicated in [Section 9.4.2](#).

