9.4.2 Management

Investigators will use clinical judgment to determine when to rescue a subject using the guidance provided in [Section 9.4.1](#) and the appropriate rescue medication to use. All rescued subjects will stop study drug at the time of rescue and will continue in the study through completion of the Visit 6 (POD22) assessments ([Table 1](#)).

If a subject needs to be rescued at Visit 5 (POD15), the Visit 5 (POD15) assessments ([Table 1](#)) should be completed before the subject is administered rescue medication.

Rescued subjects will be considered treatment failures, and the need for rescue medication will not be considered as an AE.

An AE occurring at the time of rescue will be recorded in the eCRF and will be followed by the Investigator to stabilization or resolution of the AE or the end of the study (whichever comes last).

If a subject is rescued, this event will be recorded in the eCRF (not as an AE). Medications used for rescue will be recorded in the ConMeds section of the eCRF, indicating that they were used for rescue.

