3. STUDY DESIGN

3.1 Study Design Overview

This Phase 3 study will evaluate APP13007 [REDACTED] [REDACTED] in comparison to the matching vehicle placebo in a randomized, parallel-group, double-masked fashion. Subjects will have routine uncomplicated cataract surgery on Day 0 of the study and will be assessed the next day (POD1) after the surgery for eligibility for randomization to study treatment.

Subjects who experience postoperative inflammation on POD1 and who meet all other eligibility criteria will be randomized, at a 1:1 ratio, to one of two study treatments (either Treatment 1 or Treatment 2):

[figure not shown]
- Treatment 1: 1 drop APP13007 twice daily (BID) (morning and evening) for 14 days instilled to the operated study eye
- Treatment 2: 1 drop matching vehicle placebo BID (morning and evening) for 14 days instilled to the operated study eye

After randomization, the first dose of study drug will be administered in the clinic on POD1 so that the site personnel can ensure the subject is able to administer the study drug correctly. The second drop of the study drug on POD1 will be administered by the subject a minimum of 6 hours later. For all other days, the first dose will be instilled in the morning and the second dose instilled a minimum of 6 hours, but preferably 8 to 12 hours, later. The number of drop(s) instilled and the date/time of instillation of each dose will be recorded by the subject in the subject's dosing diary. The study drug will be dosed BID for 14 days.

Any subjects who have evidence of persistent or worsening inflammation as described in the [protocol Section 9.4](#) may be rescued and placed on appropriate alternate therapy. The choice of rescue medication is at the Investigator's discretion. Rescued subjects will stop study drug and will not be withdrawn from the study. The rescued subjects will continue to be assessed at each subsequent visit, if possible, through completion of the Visit 6 (POD22) assessments.

This study will include up to 7 clinic visits (including the surgery day) over a range of 24 to approximately 52 days (Figure 1). Subjects will be discharged from the study after the assessments for Visit 6 (POD22) have been performed.

Figure 1: Study Schematic

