10.1.4 Additional Analysis

The primary efficacy endpoints will be analyzed using the data collected up to POD15. The rescued subjects will not be considered as treatment failures (Non-responders) for this analysis. All subjects' data collected up to POD15, including the data from subjects who take rescue medication, will be used to analyze the primary efficacy endpoints. Only observed data will be included to derive the primary efficacy endpoints. For the primary endpoint of ACC grade, subjects who miss one of POD 8 and POD15 assessments will be considered as treatment failures (Non-responders). For the primary endpoint of ocular pain grade, subjects who miss one of PODs 4, 8 and 15 assessments will be considered as treatment failures (Non-responders). The Pearson's Chi-square test will be used to test the treatment difference.

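### Protocol 5.4.1 allows early release of rescued subjects where other sections keep them to POD22; release before POD15 turns post-rescue responders into failures in SAP 10.1.4

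*Protocol*

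**What the plan says.** Protocol 5.4.1 states: "Rescued subjects will stop study drug and should not be withdrawn from the study". The same sentence then has them assessed through POD22 "or until the Investigator has deemed the subject is stable and can be released from the study as detailed in" Section 6.3. Section 6.3 deals with voluntary withdrawal and with discontinuation by the Investigator. It gives general discretion and an open list of reasons, but no definition of stable, no earliest visit and no release rule for rescued subjects.

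Three places are firm and offer no release:

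- Protocol 9.1.1.1: "Rescued subjects shall continue in the study and be assessed at each subsequent scheduled visit until Visit 6 (POD22").
- Protocol 9.4.2: rescued subjects "will continue in the study through completion of the Visit 6 (POD22) assessments".
- Table 1, footnote 9: rescued subjects get no more study drug or diary cards, "but will remain in the study to complete the procedures/assessments through Visit 6 (POD22").

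Two are softer. Protocol 6.2.10: "The Investigator should make every effort to keep subjects who are rescued in the study until they complete the Visit 6 (POD22) assessments". SAP 3.1: "Rescued subjects will stop study drug and will not be withdrawn from the study", with later assessments made if possible.

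On the analysis side, SAP 6.4.2 makes rescue before the POD15 assessment a failure for the primary endpoints and excludes post-rescue readings from the efficacy analyses. SAP 10.1.4 is the exception. Rescue is not failure there, and observed data to POD15 count even after rescue. For ACC, however, "subjects who miss one of POD 8 and POD15 assessments will be considered as treatment failures (Non-responders"). The pain endpoint has the same rule for PODs 4, 8 and 15.

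**The concern.** Two sites can handle the same rescued subject differently and each point to the protocol. Under 5.4.1 a subject rescued at POD4 who is quiet at POD8 may be released. Under 9.1.1.1, 9.4.2 and footnote 9 the same subject returns at POD15 and POD22.

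The difference is not neutral in SAP 10.1.4. Release depends on doing well, so the subjects lost are those whom this analysis would otherwise count as responders. Once their POD15 reading is missing they are failures again, and the result moves back towards the rescue-equals-failure result. If rescue is commoner on vehicle, the treatment difference widens for a reason unrelated to the drug. The agreement with the primary result would then be partly built in. Visits that were never made cannot be recovered at analysis.

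**Working it through.** **1. The plan's own figures.** Inputs from Protocol 10.4: ACC response 26% vs 12%, two-sided 5%, power 92%.

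n = [1.960·√(2·0.19·0.81) + 1.405·√(0.26·0.74 + 0.12·0.88)]² / 0.14² = (1.087 + 0.767)² / 0.0196 ≈ 175.5, that is 176 rounded up, against 175 stated. Power at 175 per arm is 91.9% for ACC and 94.8% for pain (57% vs 38%). With dropout, 175/0.95 = 184.2, so 185. These figures reproduce, and none depends on the release clause.

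**2. Who can be affected.** The subject must be rescued, must read ACC = 0 at POD8, would have read 0 at POD15, and must leave before the POD15 assessment. A subject with ACC > 0 at POD8 (or pain > 0 at POD4, for that endpoint) fails regardless. Release between POD15 and POD22 costs 10.1.4 nothing.

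**3. Model.** Take the planned 26% and 12% as the rates when rescue counts as failure, leaving aside dropout without rescue. Let r_a and r_v be the rescue proportions on APP13007 and vehicle, q the share of all rescued subjects who would be observed responders, and k the share of those still observed at POD15.

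Difference in 10.1.4 = (0.26 + r_a·q·k) − (0.12 + r_v·q·k) = 0.14 − (r_v − r_a)·q·k

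The documents give none of r_a, r_v, q or k. All are assumptions.

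**4. Results for ACC.**

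| r_v / r_a | q | k = 1 (all kept) | k = 0.5 | k = 0 (all released) |
|---|---|---|---|---|
| 20% / 5% | 10% | 12.5 points | 13.25 | 14.0 |
| 30% / 8% | 20% | 9.6 | 11.8 | 14.0 |
| 40% / 12% | 30% | 5.6 | 9.8 | 14.0 |
| 15% / 15% | any | 14.0 | 14.0 | 14.0 |

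Middle case, all kept: 0.26 + 0.08·0.20 = 27.6%; 0.12 + 0.30·0.20 = 18.0%; difference 9.6 points.

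Pearson p-values at these expected rates with 185 per arm, from z = difference / √(2·p̄(1 − p̄)/185):

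- 30%/8%: 0.028, 0.005 and 0.0006 for k = 1, 0.5 and 0.
- 40%/12%: 0.22 for k = 1 and 0.025 for k = 0.5. Only in this extreme row does partial release carry the result across 0.05.

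**5. The two-day rule.** SAP 6.3.5 discards efficacy readings taken more than two days after the last dose when dosing lasted under 14 days. SAP section 10 applies the 6.3.5 Analysis Visits to the efficacy analyses. Rescued subjects stop study drug at rescue, so a subject rescued at POD4 and kept to POD22 has POD8 and POD15 readings outside the rule. If it governs 10.1.4, those readings count as missing, the subject is a failure whether kept or released, and this subject's contribution is the same at k = 1 as at k = 0. The wording of 10.1.4 suggests an override but does not state one.

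**6. Completers.** SAP 10.1.3 requires Completers to complete the study, so release at any time before POD22 removes a subject from that set. If rescued Completers count as failures and all are released, rescue of 30%/8% gives 0.26/0.92 − 0.12/0.70 = 28.3% − 17.1% = 11.1 points (from unrounded rates), against 14.0 if all are kept. With these assumptions the shift is opposite to that in 10.1.4.

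**The case against.** The strongest case against giving this much weight has five parts.

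- **Peripheral analysis.** SAP 10.1.4 is an additional analysis, outside the list in 10.1.3, with no alpha attached. This stands. A reader might infer that the primary result is biased; it is not, since a rescue before POD15 is a failure with or without later visits.
- **Assumed inputs.** This also stands. A reader might take it as fact that the loss falls mainly on vehicle. That is plausible if the drug works, but no rescue rate by arm is given, and equal rates give no shift. The 20% success figure also has to average in subjects rescued at or after POD8 with cells present, who contribute nothing to ACC success.
- **Narrow route.** There is no scheduled clinic visit between POD8 and POD15, and a site must use 5.4.1 against three firm statements. This limits how often it can happen, not whether the protocol permits it.
- **Full follow-up may not be what the SAP delivers.** Because of the two-day rule, reconciling the protocol alone may not restore the data. This stands and adds to the fix.
- **Partly covered elsewhere.** Withdrawals and their reasons are tabulated by arm (SAP 7.1), so uneven release could be seen. A reader might infer that safety follow-up is lost. The loss is limited: 6.2.8 and 6.3 call for the Visit 6 assessments at early termination, 8.4 and 9.4.2 continue AE follow-up, and SAP 11.3.1 leaves post-rescue IOP to listings anyway.

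The general discretion in 6.3 might be offered as the missing rule. It lets an Investigator discontinue a subject, but sets no condition for releasing one who is stable after rescue.

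**Conclusion.** The contradiction holds as a matter of text: sites have two incompatible follow-up rules for rescued subjects, and the cross-reference leads to no release rule. The primary analysis, alpha and power are untouched.

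The statistical consequence is confined to supportive analyses. In SAP 10.1.4, release before POD15 can only pull the result towards rescue-equals-failure. Whether that widens the treatment difference depends on rescue being commoner on vehicle. Under the middle assumptions, releasing all post-rescue successes adds 4.4 points (9.6 to 14.0). Over the ranges shown with unequal rescue it adds 1.5 to 8.4 points, and with equal rescue none. These figures also assume that 10.1.4 overrides the two-day rule, which the SAP leaves open. The Completer set in 10.1.3 also depends on which rule a site follows.

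The documents do not support a claim that the trial's conclusion is at risk, or that the distortion is known to favour APP13007. They do support correcting the text, because the missing readings would be selected on good outcome and could not be recovered later.

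**What to change.** 1. Reconcile Protocol 5.4.1 with Table 1 footnote 9, 6.2.10, 9.1.1.1, 9.4.2 and SAP 3.1 so that one follow-up rule applies to rescued subjects. Correct the pointer to Section 6.3. Which rule it should be is for the sponsor to settle.
2. State in SAP 10.1.4 that the two-day rule of 6.3.5 and the post-rescue exclusion of 6.4.2 do not apply to that analysis.
3. In the 10.1.4 table, show by arm the rescued subjects with a missing required visit (POD8 or POD15 for ACC; POD4, POD8 or POD15 for pain) separately from observed failures.

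The cost is one protocol clause, one SAP sentence and one table row. Sample size and the primary analysis do not change.

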5.4.2 Prohibited Medications

The subject must provide signed informed consent before any prior medication is changed or discontinued because of participation in this study. The following medications may not be used after randomization as indicated below. If used prior to surgery (Day 0), the medications must have been used in a timeframe that equals or exceeds the minimum 'washout' period noted below.

The following medications are prohibited:

- i. Eylea® (aflibercept), Avastin® (bevacizumab), Lucentis® (ranibizumab), Beovu® (brolucizumab-dbll) or Visudyne® (verteporfin) (in either eye).
- ii. PROKERA (preserved amniotic membrane) is excluded from 1 year prior to the Screening visit to the end of the study.
- iii. Anti-inflammatory agents, analgesics (including opioids, narcotics, nonsteroidal anti-inflammatory drugs (NSAIDs), aspirin, acetaminophen and other pain medications) or immune-modulating agents systemically or in either eye from the beginning of the 'Washout' period in [Table 4](#) until after the POD15 assessments, but preferably until after the POD22 assessments. *Note: (i) acetaminophen is permitted on the day of surgery; (ii) immunizations/vaccinations are permitted before and during the study.*
- iv. Use of any of the prohibited medications listed [Table 4](#) below within a time period prior to surgery that is less than the minimum 'washout' period noted in the table.
NOTE: (i) These medications may not be used from the beginning of the 'Washout' period in [Table 4](#) until after the POD15 assessments, but preferably until after the POD22 assessments; NOTE: (ii) Medications for anesthesia related to cataract surgery, ocular pain control and non-prostaglandin-based management of raised intraocular pressure (IOP) are allowed on the day of surgery only.

v. Non-approved drugs or investigational products other than the study drug in this study are prohibited from 28 days before surgery until after the subject has been released from the study.

Table 4: Prohibited Medications and Minimum Washout Periods

Medication	Minimum 'Washout' Period Prior to Day 0
All topical ophthalmic gels or ointments	2 days
Ocular mast cell stabilizers	2 days
Ocular antihistamines	2 days
Ocular and nasal decongestants	2 days
All eye drops (except antibiotic eye drops considered to be part of pre-cataract surgery standard-of-care). Note: Antibiotics with anti-inflammatory activity and Besifloxacin Ophthalmic suspension are not permitted. Note: (i) Artificial tears are allowed, but should not be used within 10 minutes of study procedures or medication dosing; (ii) specific restrictions for ocular products are listed below.	2 days
Topical ocular corticosteroids	14 days
Topical ocular NSAIDs	7 days
Topical prostaglandin eyelash growth medications	7 days
Systemic anti-inflammatory agents including acetaminophen, NSAIDS, acetylsalicylic acid (aspirin), and Lifitegrast. Note: (i) Use of acetylsalicylic acid for cardiovascular prophylaxis (i.e., 81 mg dose QD) is allowed if dosage has been stable for at least 30 days prior to surgery and will remain stable for the duration of the study (ii) Acetaminophen may be administered as needed pre- and post-operatively on the day of surgery, (iii) Over-the-Counter preparations such as Fish Oils, Turmeric and Ginseng that may have mild anti-inflammatory effects are allowed.	7 days
Topical dermatologic corticosteroids including OTC preparations (use of topical 0.1% hydrocortisone dermal preparations for less than 3 days over a small area of skin [\sim 2 inches x \sim 2 inches] are allowed).	14 days
Systemic (oral, injectable), inhaled and/or nasal corticosteroids	21 days
Systemic analgesics/pain relievers such as gabapentin, pregabalin, opioids Note: Marijuana/CBD-containing products have the same washout restrictions as "Systemic Analgesics" because they can affect pain perception	14 days
Medications for benign prostatic hypertrophy (BPH) (e.g., finasteride, α -1 adrenergic receptor antagonists) are allowed based on the judgment of the investigator. Note: Investigators should consider the potential risk of intraoperative floppy iris syndrome in subjects who are taking or have taken α-1 adrenergic receptor antagonists (eg. tamsulosin, silodosin, alfuzosin).	Stable dose for 28 days
Topical or systemic cyclosporine	60 days
Periocular injection of corticosteroid	28 days

Medication	Minimum 'Washout' Period Prior to Day 0
Intraocular treatment with corticosteroid - dexamethasone drug delivery system	90 days after implantation
Intraocular treatment with corticosteroid – fluocinolone acetonide drug delivery system	48 months after implantation
Stable doses of anticholinergics and antidepressants are allowed. Alterations of the dose of anticholinergics and antidepressants (other than for prn use as a sleep aid) may be allowed following consultation with the Study Medical Monitor. Anticholinergic eye drops used to dilate the eye are allowed. Systemic anticholinergic drugs are allowed on the day of surgery.	See Note 1 and Note 2

Note 1

For anti-depressants used to treat depression: (i) Medication must not be washed-out for the purpose of enrollment in the study; (ii) Stable doses of anti-depressants are allowed; (iii) When the dose of an anti-depressant has been altered, the subject needs to be on the stable altered dose for at least 90 days prior to the day of surgery (Day 0).

Note 2

For anti-depressants used to treat pain: (i) The instructions provided for systemic analgesics/pain relievers apply, viz. at least a 14 day washout of the medication is required prior to the day of surgery (Day 0) continuing until the POD15 assessments have been completed.

